[name], [name], Center for Digestive Diseases, Karolinska University Hospital

[name], MD, Center for Digestive Diseases, Karolinska University Hospital

[name], MD, The surgical clinic, Stockholm South General Hospital

1:5 Report access to necessary resources during the project

Responsible for the safety of the research participants at each recruiting site:

[name], Head of Function Allied Health Professionals, Karolinska University Hospital

[name], Head of Center for Digestive Diseases, Karolinska University Hospital

[name], Head of the surgical clinic, Stockholm South General Hospital

1:6 Applications to additional authorities

NA

2. Information regarding the project

2:1 Summary of the research project

Shorter length of stay in hospitals can be a problem for older people with multiple comorbidities and functional limitations. Therefore, these patients need to be optimally prepared so that they can regain health and functional capacity as soon as possible after a planned hospital stay e.g. undergoing surgery. The aims of the project are to investigate and identify older people at high risk for complications, as well as evaluate if preoperative physical exercise can decrease the risk of complications, mortality, and prolonged length of stay in hospital after abdominal- and thoracic surgery. The observational study will include patients over the age of 70 years scheduled for surgery at Karolinska University Hospital and Stockholm South General Hospital. The association between preoperative physical activity and function and postoperative complications and length of stay will be investigated. The results from this study will form the basis for the inclusion criteria and power calculation for a randomized controlled intervention study where preoperative home-based exercise will be compared to standard preoperative care. Effects on physical function, quality of life, length of stay, complications and mortality will be studied.

2:2 Which/What scientific research questions form the basis of the project?

Observational study

Which factors can predict complications, length of stay in hospital, and mortality after abdominal and thoracic surgery, and identify older people at high risk?

Intervention study

Can preoperative exercise prior to abdominal- and thoracic surgery decrease the risk of functional decline, postoperative complications, and shorten length of stay in older people at high risk?

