Mortality, length of stay (at intensive care unit and surgical ward), discharge destination (home/or further care), delirium (with the Confusement Assessment Method), postoperative complications according to the Clavien Dindo classification and patient-reported postoperative symptoms (with the Patient-reported Postoperative Recovery Profile) will be collected. Complications such as infections, wounds, pain, respiratory support (invasive and non-invasive), need of oxygen supplement, and saturation will be documented. Suspected pneumonias will be verified with pulmonary x-ray. For data on mortality the Cause of death registry will be used, additional data will be collected from the medical records except for delirium and self-reported postoperative symptoms, which is not included in routine care. Surgical approach, duration of surgery, and type of postoperative rehabilitation will also be documented. On discharge data collection 1-6 will be repeated (see description above). Data from medical records will be collected after approval from the head of the unit according to laws and regulations.

Statistical analyses

For nominal outcomes such as mortality and discharged destination binominal logistic regression will be used. For postoperative complications according to Clavien-Dindo a multinomial regression analysis will be used with grade 1 as a reference category. Cox regression analysis will be used for analysing length of stay. For continuous outcome variables such as the measures of physical function multiple linear regressions will be used. In the analyses previously described risk factors will be controlled for (age, diabetes mellitus, heart failure, chronic pulmonary disease, systemic disease and smoking, these data are collected from the medical records).

Intervention study

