3:1 How will the selection of research participants be made?

Observational study

Patients referred to the participating clinics will be informed, orally and in writing, about the study and asked for participation by a research or contact nurse at the first visit in the surgical office.

Inclusion criteria: >70 years of age, understand and speak the Swedish language.

Exclusion criteria: Health status that contradicts physical tests of muscle strength, endurance and functional performance, or a need of acute surgery.

Intervention study

Patients referred to the participating clinics will be consecutively asked for participation in the study by a research or contact nurse at the first visit in the surgical office. For more information see below 3.1 heading Observational study.

Inclusion criteria: >70 years of age, understand and speak the Swedish language. Other inclusion criteria will be based on the results from the observational study.

Exclusion criteria: Health status that contradicts physical tests of muscle strength, endurance and functional performance, or a need of acute surgery within 7 days.

3:2 State the relationship between the researchers/test assessors and the research participants

Therapist (e.g. physician, psychologist, physiotherapist) – research participant (e.g. patient, client)

3:3 Describe the statistical basis for the sample size

For the observational study 200 participants will be recruited, based on experiences from previously published studies with similar research questions.

Power for the intervention study will be calculated based on data from the observational study. A previous study calculated power based on a 10% reduction in postoperative complications. For an 80% ($p=.05$) power, a total of 584 patients (292 per group) were to be recruited.

3:4 Is it possible that the research participants will be included in several studies at the same time or close to this time period? If so, which type of research?

The study participants will not be included in other exercise studies, however there are several medical research projects (e.g examination of surgical tissue) ongoing in parallel to this study at the participating sites. The research group will make sure that the research participants do not have a higher cumulative risk at participation.

3:5 What insurance cover the research participants?

The patient insurance legislation covers potential adverse events.

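### The Clavien-Dindo model takes grade 1 as reference, names no level for patients without a complication, and ignores the order of the grades

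*Protocol*

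**What the plan says.** Section 2:4, under the observational study's statistical analyses, fixes both the model and the reference category: "For postoperative complications according to Clavien-Dindo a multinomial regression analysis will be used with grade 1 as a reference category". The outcome is collected as "postoperative complications according to the Clavien Dindo classification", and no separate level for an uncomplicated course is named there or elsewhere.

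The only binary model in that paragraph is for other outcomes: "For nominal outcomes such as mortality and discharged destination binominal logistic regression will be used". All models are adjusted for "age, diabetes mellitus, heart failure, chronic pulmonary disease, systemic disease and smoking".

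The analysis serves the question in section 2:2: "Which factors can predict complications, length of stay in hospital, and mortality after abdominal and thoracic surgery, and identify older people at high risk". Entry does not depend on having a complication; section 3:1 gives "Inclusion criteria: >70 years of age, understand and speak the Swedish language". The sample size in section 3:3 is not derived from a formula: "For the observational study 200 participants will be recruited, based on experiences from previously published studies with similar research questions".

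**The concern.** A patient with no complication has no Clavien-Dindo grade, so a model whose lowest named level is grade 1 has no stated place for that patient. Some of the enrolled patients will have no complication, and they are the natural comparison group for a question about who develops one. The written plan leaves three ways to handle them, and none reports that comparison directly.

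Multinomial regression also treats the grades as unordered. It estimates a separate set of coefficients for each non-reference grade, in a study of 200 patients whose highest grades are likely to be sparse.

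What is at stake is the choice of risk factors. Sections 2:1, 2:4 and 3:1 let the observational results shape the inclusion criteria and possible stratification variables of the randomised trial. A predictor judged on the wrong contrast, or missed for lack of power, would carry over into who is randomised.

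**Working it through.** The protocol gives no power, effect size or grade distribution for this analysis, so there is no stated figure to reproduce. The check has three parts.

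**1. What each handling of uncomplicated patients estimates**

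- *Dropped (levels 1–5 only).* The model is conditional on having a complication. Any versus none cannot be estimated.
- *Merged with grade 1.* The contrasts are grade 2, 3, 4 or 5 against none-or-mild. Any versus none cannot be estimated.
- *Added as an extra, non-reference level.* Every printed coefficient is against grade 1. Grade k against none is recoverable as the difference of two coefficients, but it is not what the plan reports.

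The reference category alone loses nothing. Refitting one simulated data set with a different reference left the multinomial log-likelihood at −240.742 both times. The problem is the missing level and the reported contrast.

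**2. Parameter counts**

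Inputs: one predictor plus the six adjusters in section 2:4, each counted as 1 df (assumption), so 7 terms. With K levels, multinomial = (K − 1) × (7 + 1) and proportional odds = (K − 1) + 7.

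- Grades 1–5 (K = 5): 4 × 8 = 32 against 4 + 7 = 11. The predictor uses 4 df against 1.
- With a no-complication level (K = 6): 5 × 8 = 40 against 5 + 7 = 12. The predictor uses 5 df against 1.

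If 30–60% of the 200 patients have no complication (assumption), 200 × 0.70 = 140 down to 200 × 0.40 = 80 carry a grade. That is 140/32 = 4.4 down to 80/32 = 2.5 patients per multinomial parameter.

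**3. Illustrative power**

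All simulations use n = 200, one standardised predictor and data generated under proportional odds.

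- A: odds ratio 1.5 per SD, six adjusters, 150 runs; 35/50/65% uncomplicated. Wald test for the ordinal model, joint likelihood-ratio test for the multinomial.
- B: odds ratio 1.6 per SD, no adjusters, 600 runs, two-sided 0.05; 30/50/60% uncomplicated. Rank score test against the multinomial likelihood-ratio test. Assumed shares for grades 1–5 are 20/27/13/6/4%, 14/20/10/4/2% and 11/16/8/3/2% of all patients.
- C: as A in size, effect, adjusters and runs; grades 1–5 take 20/40/22/12/6% of complicated patients.

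| Handling | A | B | C |
|---|---|---|---|
| Ordinal, all patients | 89/87/79% | 94/92/91% | 85/84/77% |
| Multinomial, none added as a level | 75/64/59% | 83/78/72% | – |
| Multinomial, none merged with grade 1 | – | – | 67/66/50% |
| Multinomial, none dropped | 33/13/15% | 37/17/13% | 27/17/15% |

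In B, an ordinal model restricted to grades 1–5 had power 55/27/15%. On the literal reading, then, most of the loss comes from leaving out uncomplicated patients rather than from ignoring order. With everyone kept as a separate level, ignoring order costs 94 − 83 = 11 to 91 − 72 = 19 points in B, and 89 − 75 = 14 to 87 − 64 = 23 points in A.

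The Monte Carlo standard error is at most √(0.25/150) = 4 points in A and C and √(0.25/600) = 2 points in B.

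**The case against.** The strongest case for the plan has four parts.

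**Exclusion is not stated.** A reader might infer that the protocol drops uncomplicated patients and so loses most of its power. The text does not say so: all eligible patients are enrolled and none is removed from the analysis. The 13–37% figures belong to the literal reading only. This stands. What remains is that no level is named.

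**The contrast with none is not necessarily lost.** A reader might infer that a grade 1 reference makes comparison with an uncomplicated course impossible under every reading. It does not: if a no-complication level is kept, the comparison can be recovered from the same fit. Merging none with grade 1 also gives a usable none-or-mild comparison group, which is a reasonable way to look for high-risk patients. Both points stand, but the plan states neither handling.

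**Multinomial regression is a valid model.** It avoids the proportional-odds assumption, which is a legitimate reason to choose it, although the protocol gives no reason. All the simulations generate proportional-odds data and so favour the ordinal model; no non-proportional case was run. The grade shares are assumed, since the documents give none. This limits the size of the ordering loss, but not the fact that order is ignored.

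**Importance.** A reader might take this as the study's main outcome. The protocol names no primary outcome and lists complications alongside length of stay and mortality. A trial power calculation on complications needs an event proportion, which is descriptive and does not depend on this regression. What the model does affect is the choice of predictors, and through them inclusion criteria and stratification.

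A statistical analysis plan could add the missing level. The model and the reference category are nevertheless already fixed in the protocol, and they fit its question badly.

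**Conclusion.** The point holds as a badly fixed analysis rule and should be fixed. It is certain from the text that grade 1 is the reference, that no level is named for patients without a complication, that no any-versus-none model is planned, and that multinomial regression ignores order. None of the possible handlings directly reports which factors predict complications.

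The size depends on the handling. On the literal reading power is about 13–37%. With uncomplicated patients merged or added it is about 50–83%, against 77–94% for an ordinal model on everyone. These ranges are illustrative: they rest on assumed grade shares, 30–65% uncomplicated patients, an odds ratio of 1.5–1.6 per SD and proportional odds. The counts of 32 and 11 parameters need only the assumption of five grades, one predictor and 1 df per adjuster.

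The documents do not support the stronger conclusions that uncomplicated patients are excluded by design, that the contrast with them is lost whatever is done, or that the trial's power calculation is thereby invalid.

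**What to change.** Replace the sentence with a rule along these lines:

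- Include all patients, with no complication as the lowest (reference) category, followed by grades 1 to 5.
- Analyse the worst grade at one prespecified time chosen from the protocol's own follow-up points (discharge, 30 days or 90 days), using ordinal (proportional-odds) logistic regression with the planned adjusters.
- Prespecify one binary logistic model at a single severity cut-off, with uncomplicated patients in the lower group, as a sensitivity analysis. It should be reported in any case, not selected after a test of proportionality.
- If multinomial regression is kept, make no complication the reference and collapse the sparse high grades, with the grouping fixed in advance.

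The data collected do not change. The cost is a change to the analysis text, two choices to make in advance (follow-up time and cut-off), and the need to examine the proportional-odds assumption.

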The study is a randomized controlled study where the participants will be randomized to an intervention consisting of preoperative physical exercise or a control group following standard preoperative care. The responsible researcher will perform the randomization. The assessors of physical performance will be blinded to group allocation during the study. This is made possible, as the randomization will be conducted after the baseline assessments. The participants will also receive written information not to reveal their group allocation at follow-up assessments. The intervention period will differ depending on individual variations in preoperative waiting time, but the intervention time will be a minimum of two weeks. To optimize compliance to and quality of the exercise, the intervention will be conducted by a physiotherapist in the participants' home. The results from the observational study will form the basis for possible stratification variables in the intervention study.

Intervention group

The participants will perform individually tailored functional strength training and aerobic training, as well as inspiratory muscle training starting from 30% of maximal inspiratory capacity. On none supervised days the participants will be encouraged to follow recommendations of 30 min physical activity on moderate intensity, and inspiratory muscle training at 20% of maximal capacity. The participants will also receive usual preoperative information.

Control group

The control group will receive usual preoperative information and be encouraged to follow recommendations of 30 min physical activity on moderate intensity at least 5 days/week. Both groups will receive usual postoperative treatment and rehabilitation.

Measurements

At baseline age, sex, comorbidities, smoking habits and living situation will be collected from the medical records. The following measurements will be conducted before the intervention, after the intervention but before surgery, and at discharge from the hospital:

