Six-minute walk, gait speed, chair stands, inspiratory muscle strength, lung function, and grip strength. Mortality, length of stay, discharge destination, postoperative complications (pneumonia, stroke, wound infections, pain etc), and comorbidities will be documented after 30 days and 90 days post surgery. Need of oxygen supplement and respiratory support, and saturation will be retained from the medical records. Data from medical records will be collected after approval from the head of the unit according to laws and regulations. Possible complications or adverse events related to testing or training will be documented.

At baseline and 6 month after surgery the participants will fill in three questionnaires (sent by mail) including activities in daily living (ADL-staircase), physical activity level (PASE), and health-related quality of life (EORTC QLQ-C30). All instrument are validated and frequently used in research both nationally and internationally. Reference values from the Swedish population are to be found for the EORTC QLQ-C30.

If the study results in positive findings with decreased length of stay and improved health-related quality of life, calculations regarding health economics will be performed where the costs of preoperative exercise are put in relations to decreased length of stay.

Statistical analyses

Continuous data will be described with mean and standard deviations, and ordinal data with median and interquartile range (q1-q3). Analyses between groups will be performed with intention-to-treat (ITT) analyses and with Repeated measure ANOVA for continuous normally distributed data and Wilcoxon/Kruskal-Wallis test for ordinal data and continuous skewed data. Analyses will be performed in SPSS.

2:5 Report whether collected biological material will be stored in a bio bank

NA

2:6 Documentation, data protection and archiving

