3:6 What financial compensation or other benefits are provided to the research persons who participate in the project, and when is it paid?

No patient fee is paid by the participants in the intervention group, otherwise no financial compensation is provided.

4. Information and consent

4:1 The procedure for and the content of the information delivered to the patients at recruitment

Oral information is given in relation to recruitment for the study, if the patient is interested in participating, a written information paper will be provided. Thereafter, the patient will be contacted by the person responsible of recruitment and asked for participation. The information contain information regarding the content and procedure of the study, the research persons are also informed that they can cancel their participation at any time during the study without giving a reason or that it will affect their further care and rehabilitation. Patients who accept participation will be contacted by a physiotherapist to schedule the first assessment.

4:2 How and from who is content collected?

Written informed consent from the research person will be collected at the first assessment by the physiotherapist.

5. Ethical considerations

5:1 Describe all risks anticipated with participation

The physical assessments that will be conducted within the research project are frequently used in clinical practice, well established nationally and internationally, and do not provide any obvious risks for the participants. The choice to perform the exercise in the participants home might be perceived as an intrusion in the private sphere, however it is considered to have a small ethical impact. The value of exercising in the home setting and not having to transport themselves to a clinical is thought to outweigh possible perceptions of an intrusion in the private sphere. In frail older people physical exercise could be a risk for the individual, however previous studies have shown that the risk is small. The risk with physical inactivity is considered to be equal or higher. Close collaboration with physicians at the participating clinics will decrease the risk further.

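### The non-disclosure rule in the randomised study covers only the follow-up tests, leaving length of stay and discharge destination open to influence from knowledge of allocation on the ward

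*Protocol*

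**What the plan says.** Section 2:4 (Intervention study) sets two masking rules. The first concerns staff: "The assessors of physical performance will be blinded to group allocation during the study". The second concerns participants: "The participants will also receive written information not to reveal their group allocation at follow-up assessments". Both serve the repeated tests listed under Measurements: six-minute walk, gait speed, chair stands, inspiratory strength, lung function and grip strength.

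The same section lists outcomes that are not tests: "Mortality, length of stay, discharge destination, postoperative complications (pneumonia, stroke, wound infections, pain etc), and comorbidities will be documented after 30 days and 90 days" after surgery. Section 2:2 asks whether exercise can "decrease the risk of functional decline, postoperative complications, and shorten length of stay in older people at high risk". Length of stay also enters a planned cost analysis: "If the study results in positive findings with decreased length of stay and improved health-related quality of life, calculations regarding health economics will be performed".

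For the hospital phase 2:4 says only: "Both groups will receive usual postoperative treatment and rehabilitation". Section 5:1, on risks, adds: "Close collaboration with physicians at the participating clinics will decrease the risk further". No section says whether surgeons, nurses or ward physiotherapists are kept unaware of allocation, or who decides discharge.

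**The concern.** The protocol recognises that disclosure can distort results and guards against it, but only where a test is scored. Length of stay and discharge destination come out of care and are not scored by a blinded assessor. If those who care for the patient know that he or she has trained for some weeks, they may expect a quicker recovery. They could then discharge earlier, or to home instead of further care, without any difference in recovery.

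This is separate from bias in the tests, and blinding the test assessors does not touch it. Analysis by intention to treat does not remove it either, because the recorded stay would already contain it. It would also be hard to see afterwards. The type of postoperative rehabilitation is recorded in the observational study (2:4) but is not among the measurements listed for the randomised study.

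At stake is the reading of a shorter stay as an effect of exercise. Mortality, taken from a registry or from records, is largely unaffected.

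**Working it through.** **Coverage of the masking rules.** Set side by side:

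- Physical tests: assessor blinded, and participant asked not to disclose. Protected.
- Length of stay and discharge destination: no rule on ward staff, and no request to the participant outside the follow-up assessments. Not protected.
- One test occasion is at discharge, so the instruction reaches the end of the stay, but only for the contact with the assessor.

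**How the ward could learn the allocation.** Section 2:7 says that supervised exercise before surgery is not routinely offered, so a patient who mentions supervised home training reveals the arm. Section 5:1 plans contact with clinic physicians. In the other direction, training takes place at home (2:4), so ward staff do not necessarily see it.

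**Inputs for an illustration of size.**

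- Arm size: not fixed. Section 3:3 leaves it to the observational data. The amendment (part 3) gives 40 per arm, based on nutrient variables. Section 3:3 cites 292 per group from a previous study.
- SD of length of stay: not given. Assumed 4 to 10 days.
- Shift in mean stay from expectation alone: not given. Assumed 0.5 or 1 day.

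**The cited 292.** Section 3:3 gives a 10% reduction in complications and 80% power at p = .05, but no control rate, so the figure can be neither confirmed nor refuted. With an absolute fall from 30% to 20% and a two-sided test, n = [1.96·√(2·0.25·0.75) + 0.842·√(0.30·0.70 + 0.20·0.80)]² / 0.10² ≈ 294 per group, close to 292. It is used below only as an upper scenario.

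**False-positive rate.** For a two-sided 5% comparison of means with no true effect and a shift b:

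SE = SD·√(2/n), and rate = 1 − Φ(1.96 − b/SE) + Φ(−1.96 − b/SE).

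Example 1: SD 4, n = 40, b = 1. SE = 4·√(2/40) = 0.894 and b/SE = 1.118, so the rate is 0.200 + 0.001 = 0.201.

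Example 2: SD 10, n = 292, b = 1. SE = 10·√(2/292) = 0.828 and b/SE = 1.208, so the rate is 0.226 + 0.001 = 0.227.

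| Assumed SD (days) | Shift (days) | 40 per arm | 292 per arm |
|---|---|---|---|
| 4 | 0.5 | 9% | 33% |
| 4 | 1 | 20% | 86% |
| 6 | 0.5 | 7% | 17% |
| 6 | 1 | 12% | 52% |
| 8 | 0.5 | 6% | 12% |
| 8 | 1 | 9% | 33% |
| 10 | 0.5 | 6% | 9% |
| 10 | 1 | 7% | 23% |

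Two cautions apply. The shift is an average over the whole arm: if the ward learned the allocation of only half the exercise patients, a one-day average would need two days in each of them (1/0.5 = 2). The formula also compares means by a normal approximation, whereas 2:4 plans a rank test for skewed continuous data, so the rates show order of size only.

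**The case against.** The strongest reply is that nothing here is misstated. The sentence on non-disclosure supports blinded testing and does that job; it does not claim to mask the ward. The protocol does not say who decides discharge, so the mechanism is inferred. Training happens at home. Controls are also encouraged to be active for 30 minutes at least 5 days a week (2:4), so talk of general activity before surgery does not clearly identify an arm. All of this stands, and it makes the bias less likely. It does not close the gap: the protocol has a non-disclosure rule and limits it to occasions that leave out two of its own outcomes. This is trial conduct, which a later analysis plan cannot repair.

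Three stronger readings are tempting, and the protocol does not support them.

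- **That a discharge shift alone would be booked as a saving.** The cost calculation in 2:4 also requires improved health-related quality of life. In the randomised study that comes from questionnaires mailed 6 months after surgery, not from ward staff.
- **That the false-positive rate would be as high as the 292-per-arm column suggests.** That size belongs to a previous study. At the amendment's 40 per arm the inflation is much smaller.
- **That training notes should be kept out of ward records.** This sits badly with the contact with physicians on which 5:1 relies for safety.

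**Conclusion.** The gap is real and worth closing. The rules protect the physical tests and leave length of stay and discharge destination unprotected, although length of stay is in the research question. Knowledge of allocation could influence discharge; the protocol does not show that it will. The protocol names no primary outcome, so the weight of the point rests on the research question in 2:2 and on the part that length of stay plays in the cost analysis.

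The size is unknown. Under an assumed one-day shift, an assumed SD of 4 to 10 days and no true effect, the nominal 5% becomes about 20% to 7% at 40 per arm and about 86% to 23% at 292 per arm. The direction is the same in every scenario, but the amount depends on the assumed shift, on the SD and on a trial size not yet fixed. The observational study records length of stay, so its SD can replace the assumed one.

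**What to change.** In 2:4 (Intervention study) and in the participant information, extend the written instruction. Participants should be asked not to mention their allocation to ward staff during the hospital stay as well as at follow-up assessments, except whenever it is relevant to their health or care.

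Add one sentence saying that the study team does not tell ward staff the allocation unless this is needed for safety, and word it to agree with the contact with physicians described in 5:1.

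Optionally, record at discharge whether ward staff had learned the allocation, and report this next to the length-of-stay result. Asking staff to guess the arm would be less useful, because a true benefit would itself make guesses more often right.

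The cost is two sentences and, if wanted, one item on the discharge form. The downside is that masking on the ward will be incomplete, so the report should name this as a limitation when it interprets length of stay and discharge destination.

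### If the RCT stratifies its randomisation, the rank tests named for ordinal and skewed outcomes, notably length of stay, ignore the strata and would be conservative

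*Protocol*

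**What the plan says.** All the relevant text is in Protocol section 2:4.

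- **Randomisation (Intervention study).** "The results from the observational study will form the basis for possible stratification variables in the intervention study". No variable is named, and stratification is presented as possible, not decided.
- **RCT analysis (Intervention study, Statistical analyses).** One class of outcome is given a rank procedure: "Wilcoxon/Kruskal-Wallis test for ordinal data and continuous skewed data". The main rule, for outcomes that are roughly normal, reads: "Analyses between groups will be performed with intention-to-treat (ITT) analyses and with Repeated measure ANOVA for continuous normally distributed data". Neither strata nor covariates are mentioned.
- **RCT measurement times.** Physical function is measured "before the intervention, after the intervention but before surgery, and at discharge from the hospital". Length of stay arises only after surgery, so it has no pre-intervention value.
- **Observational analysis (Observational study, Statistical analyses).** Length of stay is analysed by Cox regression, and "In the analyses previously described risk factors will be controlled for", followed by a list: age, diabetes, heart failure, chronic pulmonary disease, systemic disease and smoking.

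Section 3:3 defers the RCT's size: "Power for the intervention study will be calculated based on data from the observational study".

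**The concern.** The observational study looks for factors that predict complications, length of stay and mortality (section 2:2). Any stratification variable drawn from it would therefore be chosen because it is prognostic. Balancing the arms on such a factor removes its contribution to chance differences between them. A test that ignores the factor still counts that variation in its standard error, so p-values are too large and intervals too wide.

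Length of stay is the outcome most exposed. It is part of the intervention research question and helps decide whether the health-economic analysis is done. If skewed, as is likely, it falls to the unadjusted rank test. With no pre-intervention value, no within-patient comparison can remove the stratum effect. What is at stake is efficiency: prognostic information gathered in 200 patients could shape the randomisation and then go unused in the test.

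**Working it through.** **Inputs.** The plan gives no power figure for this comparison. The 292 per group in section 3:3 is another study's number, stated without a control rate, and does not enter here. Assumed: two-sided 5% level (critical value 1.96); 80% power under simple randomisation, so the standardised effect is t = 1.960 + 0.842 = 2.802; perfect balance within strata; strata explaining a share R² of outcome variance. R² is not in the Protocol, so a range is shown.

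**Formulas.** After stratified randomisation the true variance of the group difference is (1 − R²) times what the unadjusted test assumes. With s = √(1 − R²):

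- excess in the standard error = 1/s − 1
- unadjusted type I error = 2Φ(−1.96/s)
- unadjusted power = Φ((t − 1.96)/s)
- adjusted power = Φ(t/s − 1.96)
- share of the possible gain lost = (adjusted − unadjusted)/(adjusted − 80%)

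**Worked case, R² = 0.20.** s = √0.80 = 0.894.

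- Type I error = 2Φ(−2.191) = 0.028.
- Unadjusted power = Φ(0.842/0.894) = Φ(0.941) = 82.7%.
- Adjusted power = Φ(2.802/0.894 − 1.96) = Φ(1.172) = 88.0%.
- Share lost = (87.95 − 82.66)/(87.95 − 80) = 5.29/7.95 = 66%.

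| Assumed R² | SE too large by | Type I error | Power, unadjusted | Power, adjusted | Share of gain lost |
|---|---|---|---|---|---|
| 0.05 | 2.6% | 4.4% | 80.6% | 82.0% | 69% |
| 0.10 | 5.4% | 3.9% | 81.3% | 84.0% | 68% |
| 0.20 | 11.8% | 2.8% | 82.7% | 88.0% | 66% |
| 0.30 | 19.5% | 1.9% | 84.3% | 91.8% | 64% |

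At R² = 0.02 and 0.40 the share lost is 70% and 59%.

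**Check by simulation: one time point.** With 40 per arm, two equal strata and R² = 0.20, the unadjusted t-test had type I error 0.0285. Power was 81.9% unadjusted and 87.4% adjusted.

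**Check by simulation: Wilcoxon.** In the same setting, type I error was 0.038, 0.028 and 0.015 at R² 0.10, 0.20 and 0.30. Stratifying raised unadjusted Wilcoxon power only from 77.0% to 78.0%, 76.4% to 78.6% and 76.1% to 78.4%. Errors within strata were normal, and a stratified rank test was not simulated. The adjusted-power column therefore indicates the gain for skewed length of stay only approximately.

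**Check by simulation: repeated-measures ANOVA.** The group-by-time contrast was represented by a two-time change score with correlation 0.7 between times (assumed) and strata affecting level only. At R² = 0.20, type I error was 0.049 and power 79.1% unadjusted against 78.9% adjusted. Nothing is lost, because subtracting each patient's own baseline already removes a stratum effect on level.

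**If randomisation is not stratified.** The unadjusted test then has its nominal 5% error and 80% power. By the same formula, adjusting for the same predictors would give about 84% at R² 0.10 and 88% at 0.20.

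**The case against.** The strongest case against is that the strata did not exist when the text was written, that the analysis paragraph only names families of tests, and that carrying strata into the model is normally left to the SAP. Much of this is fair: nobody could have listed the strata, and silence on covariates would not be a fault in itself. It does not dispose of the point, because the Protocol names a test for skewed and ordinal outcomes that in standard form cannot carry strata. An SAP that followed it would inherit the problem, and the Protocol can refer to whatever factors are used without naming them.

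Other objections stand and set the limits:

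- **A reader might infer that the RCT will stratify.** The text says only that variables are possible. The conservative error arises only if they are used.
- **A reader might infer that all the RCT tests are affected.** The group-by-time test on physical function loses nothing when strata act on level only. The Protocol does not say which ANOVA term is to be tested, and a group main effect would lack this protection.
- **R² is unknown and may be small.** The RCT's inclusion criteria are to come from the same observational results (section 3:1). Selecting on predictors would tend to narrow their range and leave less for strata to explain.
- **Nothing planned is lost.** Unadjusted power stays at or above the assumed 80% in the formula.
- **The observational adjustment does not contradict the RCT plan.** One study seeks predictors in non-randomised data and the other is randomised. The contrast shows only that an adjusted model for length of stay is already in the authors' hands.
- **Not every observational predictor is available.** The Mini Mental State Examination, Mini Nutritional Assessment, QLQ-ELD14, expiratory strength and exhaled carbon monoxide are not among the RCT baseline measurements.

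**Conclusion.** The point holds in conditional form. If randomisation is stratified on predictors from the observational study, the Wilcoxon/Kruskal-Wallis tests, chiefly for length of stay, would be conservative and forgo roughly 60% to 70% of the power that stratifying could yield. For a comparison sized at 80%, that is about 3 points at R² 0.10 (84.0 − 81.3 = 2.7) and 5 points at R² 0.20 (88.0 − 82.7 = 5.3). At R² of 0.05 it is 1.4 points. These sizes rest on an assumed R², balanced strata and normal theory. Length of stay being skewed is also an assumption, though a likely one.

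This is an inefficiency, not a threat to validity. A reader might infer bias or false-positive findings from a mismatch between design and analysis. The documents and the arithmetic support neither: the estimate is unbiased and type I error falls below 5%. The change is worth making because it costs little and is useful even without stratification.

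**What to change.** In section 2:4, Intervention study, Statistical analyses, state that:

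1. Between-group analyses include any stratification factors used at randomisation.
2. Length of stay is analysed with a stratified (van Elteren) rank test, or with the covariate-adjusted Cox model already planned for the observational study. Choose one as the main analysis; they measure the effect on different scales.
3. Any further covariates are a small set collected at RCT baseline, fixed before the first patient is randomised.
4. The unadjusted test is kept as a sensitivity analysis.

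The cost is a few degrees of freedom and slightly more analysis work. If covariates are confined to those already in the RCT baseline list, no new data are needed. Using an observational predictor outside that list would require collecting it. With the 40 per arm quoted in the amendment for the nutrition supplement, strata and covariates should be few.
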